7.11. Analysis of Efficacy

For all efficacy analyses, subjects will be analyzed in the group to which they were randomized.

7.11.1. Primary Efficacy Endpoint

The primary efficacy endpoint is whether the subject has or has not developed *S. aureus* pneumonia up to, but not including, Day 22 in the MITT Population. For the primary analysis, whether the subject has or has not developed *S. aureus* pneumonia will be based on sponsor defined outcome (SDO1).

The primary analysis is based on comparing two proportions of subjects who develop *S. aureus* pneumonia by SDO1 up to, but not including, Day 22. For each arm, the empirical proportion is defined by a ratio, which is the number of *S. aureus* pneumonia events divided by the total number of subjects in the arm. The inference about the difference of two population rates is based on the empirical counterpart. Specifically, the point estimate, 95% confidence interval and p-value for the rate difference. If subjects discontinued from the study due to any cause prior to Day 22, it will be considered as not developing *S. aureus* pneumonia by SDO1 for the primary efficacy analysis.

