### 5.2 Stratification

To ensure balance among the treatment groups, randomization for this study will be stratified by receipt or non-receipt of concomitant anti-staphylococcal antibiotics at the time of randomization that are potentially active against *S. aureus* pneumonia, including, but not limited to, nafcillin, oxacillin, vancomycin, linezolid, telavancin, ceftaroline, ceftobiprole, and teicoplanin.

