To ensure balance among the treatment groups, randomization for this study will be stratified by receipt or non-receipt of concomitant anti-staphylococcal antibiotics at the time of randomization that are potentially active against *S. aureus* pneumonia, including, but not limited to, nafcillin, oxacillin, vancomycin, linezolid, telavancin, ceftaroline, ceftobiprole, and teicoplanin.

Following randomization on Day 1, subjects will receive either a single IV dose of 3600 mg of ASN100 (comprised of separate infusions each of 1800 mg ASN-1 and 1800 mg ASN-2) or matching placebos, per their assigned randomization scheme.

If, as part of routine standard of care, additional respiratory and/or other microbiological specimens are collected for culture during the study, results will be documented within the electronic Case Report Form (eCRF). As described within the study laboratory manual, bacterial isolates recovered from these specimens that are deemed pathogens by the

Investigator (if retained and available at the study site's local microbiology laboratory) will be sent to the central microbiology laboratory for confirmation of pathogen identification (all isolates) and susceptibility testing (*S. aureus* isolates only).

Randomized subjects will be monitored daily for the signs and symptoms of pneumonia and other *S. aureus*-associated infections while hospitalized up to up to but not including Day 22.

All randomized subjects will undergo a study visit on Day 22 (+2 days) for treatment efficacy evaluation. A follow-up visit will occur on Day 28 (+2 days) to assess mortality. This visit may be conducted via telephone if the subject is no longer hospitalized.

For subjects who remain hospitalized between Day 40 and Day 90 at the institution where they received study treatment, a follow-up safety visit will be performed on the day of discharge from the hospital during this period.

All randomized subjects will return for a Safety Visit on Day 90 (± 7 days) (if the subject is unable to return to the site, this visit may be conducted by telephone). Subjects who discontinue the study prior to Day 22 will undergo an Early Termination Visit. The end of the study will occur upon completion of the last Day 90 visit by the last subject.

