4.5. Randomization and Blinding

Randomization will occur at the Randomization Visit following determination of the subject's eligibility. Subjects will be randomized via a centralized Interactive Response Technology (IRT) system in a 1:1 ratio to receive a single dose (2 infusions) of either ASN100 or matching placebo. Randomization will be stratified by receipt or non-receipt of concomitant anti-staphylococcal antibiotics at the time of randomization that are potentially effective for the treatment of *S. aureus* pneumonia.

The study follows a double-blind, placebo-controlled design. All study personnel, including investigators, site personnel, site pharmacist, Sponsor and contract research organization (CRO) staff involved in the conduct of the study (e.g., clinical research associate [CRA]/monitor), and subjects will be blinded to treatment assignment, except as described below. ASN100 and placebo will be identical in appearance to preserve blinding.

Randomization data will be kept strictly confidential until the time of unblinding and will not be accessible by subjects, Investigators, or anyone performing assessments and having access to study data until unblinding occurs. An independent Data Review Committee (as described in Section 7.6) will conduct a single interim analysis of futility assessment and will receive unblinded study data. Sponsor and CRO staff who are involved in the conduct of the study will not have access to unblinded Data Review Committee materials. The details of the interim analysis are described in the Data Review Committee Charter dated 8-June-2018. Individual subject unblinding will only occur in the case of subject emergencies or as required by regulations when reporting serious unexpected suspected adverse reactions (SUSARs), with complete unblinding at the conclusion of the study.

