7.8. Demographic and Baseline Characteristics

Demographic information including sex, race, ethnicity, corrected randomization stratification factor (receipt or non-receipt of concomitant anti-staphylococcal antibiotics at the time of randomization that are potentially active against *S. aureus* pneumonia), age (as a continuous variable and categorized as <55, 55 - <65, 65 - <75 and 75 years), height, weight, and BMI will be summarized by treatment group for the ITT, MITT, PP, PK, and Safety Populations.

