- The proportion of subjects who develop either *S. aureus* pneumonia up to but not including Day 22 as determined by the Investigator's judgement and the Review Meeting's determination of *S. aureus* as a causative pneumonia or another *S. aureus* infection up to but not including Day 22 will be obtained from Kaplan-Meier estimates for each treatment group. Discontinuation from the study due to any cause up to but not including Day 22 will be considered as an 'Event'.
 - The proportion of subjects who develop either *S. aureus* pneumonia as determined by the Investigator's judgement and the Review Meeting's determination of *S. aureus* as a causative pneumonia or another *S. aureus* infection up to but not including Day 22 will be obtained from Kaplan-Meier estimates for each treatment group incorporating censoring. Discontinuation from the study due to any cause up to but not including Day 22 will be considered censored.
 - The proportion of subjects who develop *S. aureus* pneumonia by Day 90 as determined by the Investigator's judgement will be obtained from Kaplan-Meier estimates for each treatment group. Discontinuation from the study due to any cause prior to Day 90 will be considered as an 'Event'.
 - The proportion of subjects who develop *S. aureus* pneumonia by Day 90 as determined by the Investigator's judgement will be obtained from Kaplan-Meier estimates for each treatment group incorporating censoring. Discontinuation from the study due to any cause prior to Day 90 will be considered censored.
 - In addition, the two-sided statistical test with 5% false positive rate for the treatment difference will be conducted based on the difference of two observed proportions of subjects who develop *S. aureus* pneumonia before Day 22 by both SDO1 and SDO2 populations. The treatment difference of two proportions, the corresponding 95% confidence intervals and p-values will also be provided based on a Wald test on equality of proportions.

The number and percentage of subjects with SDO1 and SDO2 of *S. aureus* pneumonia, no *S. aureus* pneumonia, indeterminate, and censored in each treatment group will be summarized descriptively.

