7.12. Subgroup Analyses

The following subgroups will be used for subgroup analyses for the primary efficacy endpoint in the MITT and PP Populations, i.e. whether the subject has or doesn't have of *S. aureus* pneumonia up to, but not including, Day 22 for both SDO1 and SDO2

populations. The exploratory efficacy endpoints, the incidence of all pneumonias, and the incidence of other non-*S. aureus* pneumonias up to, but not including, Day 22 in the MITT and PP Populations, will also undergo the following subgroup analyses.

- Corrected Randomization stratification (Receipt or Non-Receipt of concomitant anti-staphylococcal antibiotics at the time of randomization that are potentially active against *S. aureus* pneumonia.)
- Type of ICU (e.g., SICU, MICU, Neuro ICU, Trauma ICU)
- Type of mechanical ventilation (Tracheotomy or Non-Tracheotomy) at Randomization
- Length of stay in the intensive care unit (ICU) post-treatment (<5, 5-12, >12-22, and >22 days)
- Duration of mechanical ventilation before randomization (48 vs. >48 hours)
- Baseline MRSA/MSSA from qualifying ETA culture
- Pneumonia MRSA/MSSA
- Reason for mechanical ventilation
- BMI categories: <25, 25-<30, 30-<35, and 35
- Age: <50, 50-<65, and >65
- WBC $\times 10^9/L$ at Baseline: <1, 1 to <2.5, 2.5 to <5, 5 to <10, and >10
- Platelet count $\times 10^9/L$ at Baseline: <50, 50 to <150; 150 to <400, and > 400
- Change in platelet count from Baseline: decrease by 50% or greater, or an increase by 50% or greater
- Male vs. female
- Smoker vs. non-smoker
- History of COPD vs. non-COPD
- History of alcohol use vs. no history of alcohol use
- Hospital readmission within 30 days after discharge
- Qualifying ETA and Screening ETA cultures: *S. aureus* only vs. co-colonized *S. aureus* and any Gram-negative at any time before randomization vs. co-colonized *S. aureus* and any other organism at any time before randomization
- Procalcitonin at Baseline for those who develop pneumonia vs. those who don't develop pneumonia: <median vs. median
- Qualifying ETA culture: *S. aureus* 3+ vs. 4+ vs. Heavy
- Cardiac events yes/no from receipt of study drug to Day 90 or early termination
- Multi organ failure yes/no from receipt of study drug to Day 90 or early termination

- Acute kidney injury defined by an absolute increase in serum creatinine of 0.3 mg/dL or a 50% increase (*viz.*, 0.3 mg/dL increase if baseline = 0.6 mg/dL and 50% increase if baseline is = 0.6 mg/dL) within 48 hours from receipt of study drug

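### Randomisation is stratified by anti-staphylococcal antibiotic receipt, but the primary analysis ignores the stratum and no pooled stratum-adjusted analysis is planned (minor)

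*SAP*

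**What the plan says.** Protocol 5.2 states that "randomization for this study will be stratified by receipt or non-receipt of concomitant anti-staphylococcal antibiotics at the time of randomization", and SAP 4.5 repeats it: "Randomization will be stratified by receipt or non-receipt of concomitant anti-staphylococcal antibiotics at the time of randomization". SAP 4.2 gives the purpose as balance between the arms.

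SAP 7.11.1 defines each arm's rate as pneumonia events over all subjects in the arm, and adds: "The inference about the difference of two population rates is based on the empirical counterpart". The point estimate, 95% CI and p-value all follow from those two crude proportions. Section 7.11.1 names no test. The only one named for the observed proportions is at the end of SAP 7.11.2, "based on a Wald test on equality of proportions", which also has no strata. Protocol 10.2.3 mentions no strata either.

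The rest of SAP 7.11 follows the same pattern. The SDO2, ITT and PP analyses reuse the crude comparison, the Kaplan-Meier estimates are by treatment group, and the Wilcoxon tests are unstratified. SAP section 9, which lists additions to the protocol analyses, adds no adjusted analysis.

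The factor is used in two other places. SAP 7.8 tabulates the "corrected randomization stratification factor (receipt or non-receipt of concomitant anti-staphylococcal antibiotics at the time of randomization") at baseline. SAP 7.12 opens with "The following subgroups will be used for subgroup analyses for the primary efficacy endpoint in the MITT and PP Populations", and its first entry is "Corrected Randomization stratification (Receipt or Non-Receipt of concomitant" anti-staphylococcal antibiotics). Both refer to a corrected stratum, and neither says how it is corrected.

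**The concern.** When randomisation is stratified on a factor that predicts the outcome, the arms are balanced on it by design. A variance that ignores the factor then includes between-stratum variation that cannot contribute to the treatment difference. The crude interval is slightly too wide and the crude test slightly conservative.

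The subgroup analysis in SAP 7.12 gives a result within each stratum, but no combined estimate or test. A pooled analysis requested later would also require a choice between the stratum recorded in the randomisation system and the corrected one. Made after unblinding, that choice would depend on the data.

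What is at stake is a small amount of precision in a trial planned at 80% power, and the prespecification of that choice. The validity of the primary result is not in question.

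**Working it through.** **The plan's own figure.** Inputs from SAP section 6: 25% versus 12.5%, two-sided 0.05, 80% power. The unstratified pooled-variance formula, with mean rate 0.1875, is

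n = [1.960 × √(2 × 0.1875 × 0.8125) + 0.842 × √(0.25 × 0.75 + 0.125 × 0.875)]² / 0.125² = 151.9, so 152 per arm.

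Then 304 / 0.86 = 353.5, so 354 randomised. Both figures reproduce. The sample size therefore rests on an unstratified test and agrees with the planned analysis.

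**Assumptions for the gain.** The documents give neither stratum shares nor stratum event rates. The base case is equal strata, 152 per arm, an average placebo rate of 25%, and the rate halved in each stratum. The constant halving follows Protocol 1.2, which assumes the reduction regardless of antibiotic use. The stratum risk ratio (high-risk over low-risk placebo rate) is varied over 1, 1.5, 2 and 4.

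**Interval width.** The crude variance term is 0.25 × 0.75 + 0.125 × 0.875 = 0.2969. The stratified term is the average of the same expression within strata. For placebo rates of 10% and 40% it is (0.09 + 0.24)/2 + (0.0475 + 0.16)/2 = 0.2688. The narrowing is 1 − √(stratified/crude).

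**Power and size.** Simulated with 400,000 trials per cell: unpooled Wald test for the crude comparison against CMH.

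| Stratum risk ratio | Placebo rates | Stratified variance | CI narrower | Power, crude / CMH | Size, crude / CMH |
|---|---|---|---|---|---|
| 1 | 25%, 25% | 0.2969 | 0% | 0.810 / 0.807 | 0.051 / 0.050 |
| 1.5 | 20%, 30% | 0.2938 | 0.5% | 0.810 / 0.810 | 0.050 / 0.050 |
| 2 | 16.7%, 33.3% | 0.2882 | 1.5% | 0.813 / 0.817 | 0.047 / 0.050 |
| 4 | 10%, 40% | 0.2688 | 4.9% | 0.820 / 0.839 | 0.038 / 0.050 |

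The 0.3-point deficit at risk ratio 1 goes with a crude test whose size is slightly above 5%. With the Sato variance, the simulated narrowing is 0, 0.4, 1.2 and 3.9%.

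**Misrecorded strata.** At risk ratios 1, 1.5, 2 and 4:
- 10% misrecorded: interval narrower by 0, 0.3, 0.9 and 3.1%; CMH power change -0.3, -0.1, +0.2 and +1.2 points.
- 20% misrecorded: 0, 0.2, 0.5 and 1.7%; -0.3, -0.2, 0.0 and +0.5 points.

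**Unequal strata, no misrecording.** With 10, 30, 70 and 90% of subjects in the low-risk stratum:
- Risk ratio 2: CMH power change -0.1, +0.2, +0.5 and +0.2 points.
- Risk ratio 4: 0.0, +0.9, +3.0 and +2.9 points.

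CMH size stays at 0.049 to 0.051 across these shares. At a 10% share and risk ratio 4, the smallest stratum-by-arm cell expects only 0.5 events, so sparse cells are possible.

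**Separate check.** A second simulation (200,000 trials per scenario, 25, 50 or 75% of subjects on antibiotics) varied the absolute gap in placebo rate between strata. CMH changed power by -0.3 to 0.0 points at gaps up to 10 percentage points, +0.5 to +0.7 at 20, and +1.4 to +2.0 at 30.

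**The case against.** The strongest reply is that nothing is wrong. Stratification was introduced for balance and achieves that without an adjusted test. The documents promise no adjusted analysis, and the sample size matches the crude one. All of this is true.

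The evidence in the documents also points to a small gain. Protocol 1.2 reports that patients on potentially effective antibiotics still developed pneumonia, and that secondary analyses found antibiotics ineffective at preventing it. If the factor is that weakly prognostic, CMH gains nothing or loses about 0.3 points. The larger gains need a fourfold stratum risk ratio, which nothing in the documents supports. This stands, and it is why the point is minor.

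The proposed interval is slightly liberal. Under a 25% null rate with equal strata it excludes zero in about 5.3% of trials, against 5.1% for the crude Wald interval when the strata do not differ. Paired with a CMH p-value, it can also disagree with the test, in roughly 0.5 to 0.65% of trials under the design alternative. Both effects are real but too small to change the recommendation, and the CMH p-value itself holds 5%.

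Finally, the subgroup counts would let a reader compute a pooled result. That would not be a prespecified analysis, and the choice of stratum would still be open.

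**Conclusion.** The point holds as a minor one. Randomisation is stratified, the primary inference is crude, and neither document plans a pooled stratum-adjusted efficacy analysis. The crude analysis remains valid; it becomes conservative only if antibiotic receipt is strongly prognostic, with size falling to about 3.8% at a stratum risk ratio of 4.

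With equal, correctly recorded strata, the change in power from CMH runs from -0.3 to +1.9 points. It reaches +3.0 points in the most favourable share examined. These figures rest on assumed stratum shares, risk ratios and misrecording rates, so the gain is possible but not shown. The case for the change is that its downside is negligible and its cost low. The Population and Outcome Plan and the committee charter were not available, so the statement covers the protocol and SAP only.

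**What to change.** In SAP 7.11.1, state that the primary risk difference and 95% CI will be Mantel-Haenszel weighted across the two antibiotic strata, with the variance taken from the within-stratum proportions, and that the p-value will come from a CMH test with the same strata. State before unblinding whether the stratum recorded in the randomisation system or the corrected stratum is primary, and use the other as a sensitivity analysis. Apply the same method to the SDO2, ITT and PP analyses, and report the crude difference as supportive.

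This makes the stratified analysis primary, so it should be listed in SAP section 9. A short rule for sparse strata is also sensible, as is a check that the futility evaluation described in the charter remains consistent.

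The core change is two sentences, and SAP section 3 allows modification before unblinding. No new data are needed, because the factor is already recorded for randomisation and for the planned subgroup analysis. The one substantive decision is which version of the stratum to use.

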7.11.2. Additional Analyses for *S. aureus* Pneumonia

Analyses of the primary efficacy endpoint will also be performed based on the ITT and PP Populations.

The following additional analyses will be performed in the MITT and PP Populations:

- The primary efficacy analysis, based on comparing two proportions of subjects who develop *S. aureus* pneumonia by SDO2 up to, but not including, Day 22. If subjects discontinued from the study due to any cause prior to Day 22 it will be considered as not developing *S. aureus* pneumonia for this analysis by SDO2.
- The primary analysis is based on comparing two proportions of subjects who develop *S. aureus* pneumonia by SDO1 up to, but not including, Day 22. For each arm, the empirical proportion is defined by a ratio, which is the number of *S. aureus* pneumonia events divided by the total number of subjects in the arm. The inference about the difference of two population rates is based on the empirical counterpart. Specifically, the point estimate, 95% confidence interval and p-value for the rate difference. If subjects discontinued from the study due to any cause prior to Day 22, it will be considered as developing *S. aureus* pneumonia by SDO1 and SDO2.
- The Kaplan-Meier analysis will be performed for the proportion of subjects who develop *S. aureus* pneumonia by Day 21 as determined by SDO1. The proportion of subjects who develop *S. aureus* pneumonia up to but not including Day 22 will

be obtained from Kaplan-Meier estimates for each treatment group. The inference about the difference of two rates will be made via the Kaplan-Meier estimates and their corresponding variance estimates in the MITT population. The treatment difference of two rates, the corresponding 95% confidence intervals and p-value will be presented. In addition, the number and percentage of subjects who developed *S. aureus* pneumonia or were censored will be summarized. The Kaplan-Meier estimate of event rates evaluated at Day 21 and the corresponding 95% confidence intervals will be presented for each treatment group. Subjects who did not develop *S. aureus* pneumonia, discontinued from the study, or died prior to Day 22 will be considered censored. For the censored subjects, the last assessment date on which the subject did not develop *S. aureus* pneumonia based on the Investigator's assessment will be used as the date of censoring.

- The Kaplan-Meier analysis will be performed for the proportion of subjects who develop *S. aureus* pneumonia up to but not including Day 22 as determined by SDO1 and the Review Meeting's determination of *S. aureus* as a causative pneumonia pathogen.
- The Kaplan-Meier analysis will be performed for the proportion of subjects who develop *S. aureus* pneumonia up to but not including Day 22 as determined by SDO2 and the Review Meeting's determination of *S. aureus* as a causative pneumonia pathogen
- The Kaplan-Meier analysis will be performed for the proportion of subjects who develop *S. aureus* pneumonia up to but not including Day 22 as determined by the Investigator's judgement and the Review Meeting's determination of *S. aureus* as a causative pneumonia pathogen.
- An additional Kaplan-Meier analysis will be conducted for subjects with *S. aureus* pneumonia and presumed *S. aureus* pneumonia by SDO1 and SDO2. The presumed *S. aureus* pneumonia population includes those subjects with microbiologic results "Not Done" up to and including Day 7 (presumed *S. aureus* pneumonia).
- A third Kaplan-Meier analysis will be conducted for subjects with *S. aureus* pneumonia including those subjects with microbiologic results "Not Done" up to and including Day 10 (presumed *S. aureus* pneumonia) for both SDO1 and SDO2 populations.
- The proportion of subjects who develop *S. aureus* pneumonia up to but not including Day 22 as determined by the Investigator's judgement and the Review Meeting's determination of *S. aureus* as a causative pneumonia pathogen will be obtained from Kaplan-Meier estimates for each treatment group. Discontinuation from the study due to any cause up to but not including Day 22 will be considered as an 'Event'.
- The proportion of subjects who develop *S. aureus* pneumonia up to but not including Day 22 as determined by the Investigator's judgement and the Review Meeting's determination of *S. aureus* as a causative pneumonia pathogen will be

- obtained from Kaplan-Meier estimates for each treatment group incorporating censoring. Discontinuation from the study due to any cause up to but not including Day 22 will be considered censored.
- The proportion of subjects who develop either *S. aureus* pneumonia up to but not including Day 22 as determined by the Investigator's judgement and the Review Meeting's determination of *S. aureus* as a causative pneumonia or another *S. aureus* infection up to but not including Day 22 will be obtained from Kaplan-Meier estimates for each treatment group. Discontinuation from the study due to any cause up to but not including Day 22 will be considered as an 'Event'.
 - The proportion of subjects who develop either *S. aureus* pneumonia as determined by the Investigator's judgement and the Review Meeting's determination of *S. aureus* as a causative pneumonia or another *S. aureus* infection up to but not including Day 22 will be obtained from Kaplan-Meier estimates for each treatment group incorporating censoring. Discontinuation from the study due to any cause up to but not including Day 22 will be considered censored.
 - The proportion of subjects who develop *S. aureus* pneumonia by Day 90 as determined by the Investigator's judgement will be obtained from Kaplan-Meier estimates for each treatment group. Discontinuation from the study due to any cause prior to Day 90 will be considered as an 'Event'.
 - The proportion of subjects who develop *S. aureus* pneumonia by Day 90 as determined by the Investigator's judgement will be obtained from Kaplan-Meier estimates for each treatment group incorporating censoring. Discontinuation from the study due to any cause prior to Day 90 will be considered censored.
 - In addition, the two-sided statistical test with 5% false positive rate for the treatment difference will be conducted based on the difference of two observed proportions of subjects who develop *S. aureus* pneumonia before Day 22 by both SDO1 and SDO2 populations. The treatment difference of two proportions, the corresponding 95% confidence intervals and p-values will also be provided based on a Wald test on equality of proportions.

The number and percentage of subjects with SDO1 and SDO2 of *S. aureus* pneumonia, no *S. aureus* pneumonia, indeterminate, and censored in each treatment group will be summarized descriptively.

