Semi-quantitative cultures using chromogenic media are preferred for determination of eligibility for randomization; however, any quantitative or semi-quantitative culture performed that indicates that a subject is heavily colonized with *S. aureus* is permitted if the culture results are available to randomize the subject within 48 hours (or up to 60 hours with Medical Monitor approval) from the time the ETA specimen was collected.

Once an enrolled subject has an ETA culture reported positive for heavy *S. aureus* colonization and meets all of the inclusion and none of the exclusion criteria, they are eligible for randomization. If they are not randomized on this occasion according to the protocol, they are no longer eligible for continued ETA sampling or randomization, and will be discontinued from the study; however, if subjects are extubated and subsequently re-intubated/mechanically ventilated, they are eligible for re-screening as a new subject enrollment, provided all entry criteria continue to be met. Subjects who were previously randomized are not eligible to be re-consented and re-screened.

At the time of randomization, if a subject's screening ETA culture also shows heavy colonization of a Gram-negative organism (i.e. heavy co-colonization of both Gram-positive and Gram-negative organisms), the subject will not be randomized into the study; however, randomization should not be delayed while waiting for Gram-negative results if heavy colonization with *S. aureus* has been confirmed. Testing for Gram-negative colonization is however not a requirement of the study protocol and would apply to centers that routinely test for both Gram-positive and Gram-negative organisms as part of standard of care.

Nasal swab specimens (one from each nostril) will be obtained at the Randomization Visit and will be cultured by the central microbiology laboratory. Results from the nasal swab specimen cultures will be used to assess correlation with results of the qualifying ETA culture.

Upon determination of eligibility, approximately 354 subjects will be randomized in a 1:1 ratio to 1 of 2 treatment groups:

- ASN100 administered as 2 separate intravenous (IV) infusions of ASN-1 and ASN-2 either sequentially or simultaneously, or
- Placebo administered as 2 separate IV infusions either sequentially or simultaneously.

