5.2.2. Sponsor-Defined Outcome of *S. aureus* Pneumonia

Sponsor-Defined Outcome (SDO) of *S. aureus* pneumonia will be determined programmatically based on the data and the manual review conducted at Review Meetings per the POP.

Each randomized subject will be evaluated for the occurrence of *S. aureus* pneumonia between Randomization and up to, but not including, Day 22. In order to assign a SDO, the following assessments will be made based on available data:

1. Microbiological Assessment
2. Chest Imaging Assessment
3. Clinical Assessments
 - a. Respiratory
 - b. Signs and Symptoms
4. Operational Assessments

There will be 2 SDO definitions for data analysis: SDO1 and SDO2. The 2 definitions will need to satisfy the 4 assessments above and differ only on the clinical assessments. SDO1 will meet either respiratory OR signs and symptoms requirements while SDO2 will meet both respiratory AND signs and symptoms requirements.

The individual assessments for each randomized subject will be collapsed to assign an SDO1/SDO2 of Yes, No, Indeterminate (i.e. insufficient data to assign a SDO of Yes or No), or Censored (i.e. subject died prior to the Day 22 assessment) based on the mutually exclusive, hierarchical rules specified in the POP.

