6. SAMPLE SIZE DETERMINATION

The estimated incidence of progression to *S. aureus* pneumonia in mechanically ventilated subjects with heavy endotracheal colonization of *S. aureus* is approximately 25% within 22 days of randomization.

Assuming a 2-sided significance level of 0.05 and a desired power of 80% to detect a significant difference between *S. aureus* pneumonia incidence rates of 25% in the placebo group and 12.5% in the ASN100 treatment group (50% reduction), 152 evaluable subjects are required in each treatment group. A sample size of 304 subjects (152 subjects per treatment group) will yield 80% power to detect a 50% reduction in the incidence of *S. aureus* pneumonia with ASN100 treatment when assuming a 25% incidence rate of *S. aureus* pneumonia in placebo-treated subjects. Assuming a 14% non-evaluable rate, approximately 354 subjects (177 subjects per treatment group) will be randomized. Assuming the screen failure rate is about 84%, approximately 2250 subjects will be screened.

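### The additional SDO1 Kaplan-Meier analysis takes its event from SDO1 but its censoring date from the Investigator, so some subjects classified SDO1 No can be censored early and informatively

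*SAP*

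**What the plan says.** The first Kaplan-Meier bullet in SAP 7.11.2 estimates the proportion with S. aureus "pneumonia by Day 21 as determined by SDO1". It reports a treatment difference, a 95% confidence interval and a p-value. Subjects who did not develop S. aureus "pneumonia, discontinued from the study, or died prior to Day 22 will be considered censored". Their date is the last assessment on which they had not developed it, and this date "based on the Investigator's assessment will be used as the date of censoring".

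SAP 5.2.2 says that the sponsor-defined outcome "will be determined programmatically based on the data and the manual review conducted at Review Meetings per the POP". It draws on microbiological, chest imaging, clinical and operational assessments, covers randomization to before Day 22, and has four values: Yes, No, Indeterminate (insufficient data) and Censored (death before the Day 22 assessment).

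SAP 5.2.1 leaves the diagnosis of pneumonia to the Investigator's own clinical judgement. SAP 7.3.2 says that subjects without an SDO1 or SDO2 event are censored in the Kaplan-Meier analysis, but gives no date.

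**The concern.** Event and censoring date come from two different determinations. Suppose the Investigator diagnoses S. aureus pneumonia on Day 6 and SDO1 is No, for example because the specimen culture or the chest image did not meet the SDO1 requirement. Read naturally, the rule censors this subject on about Day 5. Yet No is a classified outcome for the whole window, because insufficient data and death have their own categories.

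Kaplan-Meier assumes that a censored subject carries the same future risk as those who stay under observation. This subject is classified as having no SDO1 event. Removing the subject shrinks the denominator for later events without removing any event, so 1-KM rises. The trigger is a diagnosis closely related to the event, so the censoring is informative.

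This analysis censors discontinuations, whereas the primary analysis counts them as non-events. A reader will therefore use it to judge how sensitive the primary result is to dropout. As written, the two results could differ because of disagreement over diagnosis rather than because of dropout.

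**Working it through.** **Inputs from SAP section 6.** Two-sided 0.05, 80% power; "pneumonia incidence rates of 25% in the placebo group and 12.5% in the ASN100 treatment group (50% reduction), 152 evaluable subjects are required" in each group. "Assuming a 14% non-evaluable rate, approximately 354 subjects (177 subjects per treatment group) will be randomized".

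**Reproducing the plan's figure.** Pooled-variance formula without continuity correction:

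n = [1.960 × √(2 × 0.1875 × 0.8125) + 0.842 × √(0.25 × 0.75 + 0.125 × 0.875)]² / 0.125² = 151.9, so 152 per arm (power 80.0%). Then 304 / 0.86 = 353.5, so 354 randomized. The plan's sample size reproduces. It gives no figure for the censoring rule.

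**Effect of the rule by hand.** Let N be the arm size, E the SDO1 events, k the events up to the censoring day and c the discordant subjects censored on that day. With no other censoring before Day 21,

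1-KM = 1 − [(N − k)/N] × [(N − c − E)/(N − k − c)].

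With c = 0 this is E/N: 38/152 = 25.0% and 19/152 = 12.5%. The difference is 12.5 points (SE 4.4, z 2.83).

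Now assume that 15 of 152 per arm (about 10%) are discordant and censored on Day 5, with events spread evenly over Days 2 to 21:

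- Placebo, k = 8: 1 − (144/152) × (99/129) = 27.3%.
- ASN100, k = 4: 1 − (148/152) × (118/133) = 13.6%.
- Difference: 13.7 points (z 2.86).
- Discordance in the ASN100 arm only: 25.0 − 13.6 = 11.4 points (z 2.50).
- Discordance in the placebo arm only: 27.3 − 12.5 = 14.8 points (z 3.19).

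**Wider range, all assumed.** Censoring on Day 3, 5 or 10, with events either even or front-loaded:

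| Discordance | Day 21 rates, placebo / ASN100 | Difference (points) | z |
|---|---|---|---|
| None | 25.0% / 12.5% | 12.5 | 2.83 |
| Equal, 5 to 20% per arm | from 25.3% / 12.7% to 30.7% / 15.3% | 12.7 to 15.4 | 2.82 to 2.92 |
| Unequal, 5% vs 15% or 0% vs 10%, either direction | | 11.3 to 16.0 | 2.45 to 3.28 |

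**Simulation of a single arm.** 400,000 subjects; true SDO1 incidence 25%; event and discordant-diagnosis days exponential with mean 6 days, capped at Day 21; discordant subjects censored the day before diagnosis; no other censoring.

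| Discordant subjects (assumed) | Reported 1-KM |
|---|---|
| 5% | about 25.7% |
| 10% | about 26.6% |
| 15% | about 27.5% |
| 20% | about 28.5% |

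Two arms with the same true 25% but 5% and 15% discordance would appear to differ by 27.5 − 25.7 = 1.8 points. With equal discordance both arms rise alike, and no false difference appears.

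**The case against.** The strongest reply is that the phrase only names the source of dated assessments. Investigators assess subjects daily, whereas SDO1 is assigned afterwards. For anyone the Investigator never diagnosed, the date is already the last monitoring assessment. The rule also says last assessment, not the day before the first diagnosis, so after a resolved episode the date could fall near Day 21. That reading is possible and would lessen the early removal, but the SAP does not state it.

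Several further limits stand.

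- Some discordant subjects, such as those with no adequate specimen culture, may be Indeterminate rather than No. The rules that decide this are in the Population and Outcome Plan, which is not among the documents.
- Which Investigator call sets the date is unclear. In most of the Investigator-judged analyses the Review Meeting attributes the pneumonia to S. aureus.
- The discordance rates are assumed, and the higher ones are demanding. If every SDO1 event is also Investigator-positive, 10% and 20% discordance mean that SDO1 rejects 10/35 = 29% and 20/45 = 44% of Investigator-positive subjects.
- Assessors and outcome review are blinded, and nothing in the documents predicts unequal discordance.

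A reader might infer more than the documents support:

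- **That the primary result is biased.** It is not. SAP 7.11.1 uses the simple SDO1 proportion over all subjects in the arm, with no censoring date.
- **That a spurious treatment effect has been shown.** It has not; that needs discordance to differ between arms.
- **That discordance is the only thing that shrinks the risk set.** Deaths and discontinuations before Day 22 are also censored.
- **That the rule governs every SDO1 and SDO2 Kaplan-Meier analysis.** The date is stated only in this one bullet.

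**Conclusion.** The point holds for the additional SDO1 Kaplan-Meier analysis on the natural reading of the text. It is a stated rule that can give a wrong estimate, not merely a missing detail, and nothing in the SAP or protocol overrides it. The direction is upward for 1-KM in each arm that has discordant subjects.

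The size is unknown because no discordance rate is given. At 5 to 10% discordance the simulated rise is 0.7 to 1.6 points on a true 25%; at 20% it is 3.5 points. At the planned rates, equal discordance enlarges the difference but barely moves z. Only unequal discordance changes the inference noticeably.

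These figures assume early censoring of discordant subjects, complete SDO1 classification for them, and no other loss to follow-up. The matter should be settled before unblinding, but it does not threaten the primary analysis.

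**What to change.** Replace the censoring-date sentence in SAP 7.11.2 with a rule tied to the outcome being analysed:

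- Censor subjects classified SDO1 No with complete follow-up at Day 21.
- Censor indeterminate, discontinued or deceased subjects at the last date on which SDO1 could be assessed.
- State that any SDO2 Kaplan-Meier analysis uses the matching SDO2 rule.
- Keep the Investigator-based date only for the Investigator-judged analyses, and say there which Investigator call sets it.

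The rule should be checked against the Population and Outcome Plan so that No and Indeterminate are used consistently. The cost is a short SAP edit and one changed derivation, with no new data. A table of Investigator diagnosis against SDO1 by arm would show how much the choice matters.
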